## 5.2.4 Electrocardiogram

The 12-lead ECGs must be administered by a qualified technologist and results will be recorded as scheduled in the Flow Chart. The investigator or a designee will evaluate whether the ECG is normal or abnormal and assess clinical relevance. ECGs may be repeated for quality reasons and a repeated recording used for analysis. Additional ECGs may be recorded for safety reasons. Dated and signed printouts of ECG with findings should be documented in patient's medical record.

For AE reporting of clinically relevant abnormal findings please refer to [Section 5.2.6.2](#).

## 5.2.5 Other safety parameters

All cases of malignancies that are detected during the trial will be reported as SAEs. Patients with a history of malignancy (except for specific cancers) will be excluded from this trial per the exclusion criteria ([Section 3.3.3](#)). For correct AE reporting in this extension trial refer to [Section 5.2.6.2](#).

## 5.2.6 Assessment of adverse events

### 5.2.6.1 Definitions of AEs

#### 5.2.6.1.1 Adverse event

An AE is defined as any untoward medical occurrence in a patient or clinical investigation subject administered a medicinal product and which does not necessarily have to have a causal relationship with this treatment.

An AE can therefore be any unfavourable and unintended sign (including an abnormal laboratory finding), symptom, or disease temporally associated with the use of a medicinal product, whether or not considered related to the medicinal product.

The following should also be recorded as an AE in the CRF and BI SAE form (if applicable):

- Worsening of the underlying disease or of other pre-existing conditions
- Changes in vital signs, ECG, physical examination and laboratory test results, if they are judged clinically relevant by the investigator.

For AE reporting of abnormalities refer to [Section 5.2.6.2](#).

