#### 2.1.2 Primary endpoint(s)

The primary endpoint is the occurrence of treatment emergent adverse events (TEAEs) up to week 260 of maintenance treatment.

Note: TEAEs are defined as all adverse events occurring between start of treatment in the extension trial and the end of its residual effect period. Adverse events that start before first drug intake in the extension trial and deteriorate under treatment during the extension trial will also be considered as 'treatment-emergent'.

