#### 3.3.2 Inclusion criteria

Each patient must meet all of the following inclusion criteria to be included into the trial:

1. Signed and dated written informed consent for the current trial 1368-0024, in accordance with ICH-GCP and local legislation prior to admission to the current trial
2. Male or female patients who have completed the treatment period in one of the parent trials without premature discontinuation
3. Patients who have obtained an individual health benefit, per investigator judgement (**e.g.** PPP PGA of 0 (clear) or 1 (almost clear) or other clinical improvement), from treatment in the parent trial.
4. Women of childbearing potential must be ready and able to use highly effective methods of birth control per ICH M3 (R2) that result in a low failure rate of less than 1% per year when used consistently and correctly. A list of contraception methods meeting these criteria is provided in [Section 4.2.3](#) and in the patient information. *Note: A woman is considered of childbearing potential, i.e. fertile, following menarche and until becoming postmenopausal unless permanently sterile. Permanent sterilisation methods include hysterectomy, bilateral salpingectomy and bilateral oophorectomy. Tubal ligation is not a method of permanent sterilization. A postmenopausal state is defined as no menses for 12 months without an alternative medical cause.*

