#### 3.3.4.1 Wish to discontinue trial treatment, non-compliance of patient, medical reason and intake of restricted medication

An individual patient will be withdrawn from the trial if:

- The patient wants to discontinue trial treatment, without the need to justify the decision. This includes patients losing individual perceived health benefit or becoming aware of a preferred treatment option.
- The patient has repeatedly shown to be non-compliant with important trial procedures and, in the opinion of both, the investigator and sponsor representative, is not willing or able to adhere to the trial requirements in the future.
- The patient can no longer receive trial treatment for medical reasons (such as surgery, adverse events – see also [Section 3.3.4.3](#), other diseases, or pregnancy). The patient took restricted medication which is not allowed acc. to [Section 4.2.1](#) and [Table 4.2.1: 1](#).

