#### 3.3.4.2 Implications due to loss of treatment response

- Patients who need to take rescue medication must be discontinued from the trial. Rescue therapy is defined as the use of topical corticosteroids or other topical treatment, systemic immunomodulating treatments or biologics and therapy such as tonsillectomy, for the treatment of worsening of PPP. For the complete list and all details of restricted medication see [Section 4.2.1](#) and [Table 4.2.1: 1](#).
- The following additional trial treatment discontinuation criteria apply from Visit 2 onwards:
  - Increase of pustulation severity compared to baseline (baseline (V1) of extension trial)AND
  - Loss of PPP ASI by  $\geq 5$  points compared to baseline (baseline (V1) of extension trial)

A patient who meets the trial treatment discontinuation criteria at 2 consecutive visits must be discontinued from the trial treatment and administered standard of care therapy.

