An overall summary of AEs will be presented. This overall summary will include summary statistics for the class of other significant AEs (sponsor definition based on ICH E3) and for the class of AESIs.

Based on the specification provided in ICH E3 (8), the sponsor has defined AEs which are to be classified as 'other significant'. For the current trial, these will include those non-serious AEs which were reported with 'action taken = Drug withdrawn' or 'action taken = Dose reduced'.

The following is considered an AESI in this trial (see Section 5.2.6.1.4 in CTP):

- Systemic hypersensitivity reactions including anaphylactic reaction
- Severe infections (according to RCTC grading in CTP Appendix 10.3)
- Opportunistic and mycobacterium tuberculosis infections
- Hepatic injury

A hepatic injury is defined by the following alterations of hepatic laboratory parameters:

- *an elevation of AST (aspartate transaminase) and/or ALT (alanine aminotransferase) ≥ 3 fold ULN combined with an elevation of total bilirubin ≥ 2 fold ULN measured in the same blood draw sample, or*
- *aminotransferase (ALT, and/or AST) elevations ≥ 10 fold ULN.*

- Peripheral Neuropathy

The investigator had to classify on the eCRF whether an observed AE was an AESI or not.

In addition, user defined adverse event concepts (UDAEC) identified through specific search criteria will be reported separately (see [Table 7.8.1: 1](#)).

Table 7.8.1: 1 Project MEDDRA search criteria for User Defined Adverse Events Concepts

User-defined AE category		
	Label	Description
Infections (serious/severe, opportunistic)	Infections ALL	Combined search strategy based on the individual UDAECs described below; the UDAEC “severe infections (investigator-defined) will be disregarded for this search
	Opportunistic infections	Narrow SMQ “Opportunistic infections”
	Tuberculosis infections	BIcMQ “Infections”: Narrow sub-search 8.2 “Tuberculosis related terms”
	Serious infections	all serious events in SOC “Infections and infestations”
	Severe infections	all events in SOC “Infections and infestations” of at least severe RCTC grade, by HLG
	Hypersensitivity	Hypersensitivity ALL
Anaphylactic reaction		Narrow SMQ “Anaphylactic reaction”
Angioedema		Narrow SMQ “Angioedema”
Hypersensitivity		Narrow SMQ “Hypersensitivity”
Malignancies	Malignant tumours	Narrow Sub-SMQ “Malignant tumours” Narrow Sub-SMQ “Haematological malignant tumours” Narrow Sub-SMQ “Non-Haematological malignant tumours”

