	Malignant skin tumours	Broad Sub-SMQ “Skin malignant tumours”
	Skin melanomas	HLT Skin melanomas (excl. Ocular)
	Non-melanoma skin cancer (NMSC)	Broad Sub-SMQ “Skin malignant tumours” excluding HLT Skin melanomas (excl. Ocular)
	Malignancies excluding NMSC	Sub-SMQ “Malignant tumours” excluding NMSC, whereas NMSC is defined above
	3-point MACE	3-point MACE

Table 7.8.1: 1 Project MEDDRA search criteria for User Defined Adverse Events Concepts (continued)

	Label	Description
Torsades de Pointes	Torsades de Pointes	Broad sub-SMQ “Torsade de pointes/QT prolongation”
DRESS	DRESS (Drug reaction with eosinophilia and systemic symptoms syndrome), broad	Algorithmic SMQ on "Drug reaction with eosinophilia and systemic symptoms syndrome", broad Algorithm: A or (B and C and D) or (B and C and E) or (B and D and E)
	DRESS (Drug reaction with eosinophilia and systemic symptoms syndrome), narrow	SMQ “Drug reaction with eosinophilia and systemic symptoms syndrome”, narrow
Peripheral neuropathy	Peripheral neuropathy	SMQ “Guillain-Barre syndrome”, narrow; SMQ “Demyelination”, narrow; SMQ “Peripheral neuropathy”, narrow

* this is achieved by retrieving all cases found either by running subsearch 1 in narrow scope (BlcMQ search ID 32019093) or subsearch 2 (BlcMQ search ID 32019094)

The exposure-adjusted incidence rate and frequency of patients with AEs will be summarized by primary system organ class and preferred term. AEs which were considered by the investigator to be drug related will be summarised separately. Separate tables will also be provided for patients with SAEs, patients with AESIs, patients with AE leading to discontinuation of the trial medication, and patients with other significant AEs (as described previously) and User-defined Adverse Event Concepts (UDAEC) (See [Table 7.8.1: 1](#)). AEs will also be summarized by maximum intensity based on the RCTC measure (see [Section 5.4.1](#)).

For disclosure of AE data on ClinicalTrials.gov, the frequency of patients with non-serious AEs occurring with an incidence of greater than 5 % (in preferred terms) will be summarised by primary system organ class and preferred term. The frequency of patients with SAEs and drug related SAEs will also be summarised respectively.

For disclosure of AE data in the EudraCT register, the frequency of non-serious AEs with an incidence of greater than 5 % (in preferred terms) and the frequency of SAEs will be summarised.

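### Worsening of PPP counts as an adverse event, so the overall TEAE lines, and depending on site coding the AE-discontinuation lines, could mix loss of efficacy with harm

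*Protocol*

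**What the plan says.** **What counts as an AE.** Protocol 5.2.6.1.1 lists, among the things to record as an AE, "Worsening of the underlying disease or of other pre-existing conditions". The readable text makes no exception for PPP.

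**Primary endpoint.** Protocol 2.1.2: "The primary endpoint is the occurrence of treatment emergent adverse events (TEAEs) up to week 260 of maintenance treatment". SAP 5.1 repeats this and refers to SAP 7.8.1 for the exposure-adjusted rates.

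**Who enters.** Inclusion criterion 3 (Protocol 3.3.2) admits "Patients who have obtained an individual health benefit, per investigator judgement". Treatment then runs for up to 260 weeks.

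**When treatment must stop.** Protocol 3.3.4.2 has two mandatory routes. One is rescue: "Patients who need to take rescue medication must be discontinued from the trial". The other is a rise in pustulation severity together with a loss of at least 5 PPP ASI points against the extension baseline: "A patient who meets the trial treatment discontinuation criteria at 2 consecutive visits must be discontinued from the trial treatment".

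**What is tabulated.** SAP 7.8.1 counts patients, not events. It plans an overall AE summary, exposure-adjusted rates, and separate tables that include "patients with AE leading to discontinuation of the trial medication, and patients with other significant AEs". On the other significant AEs it says "these will include those non-serious AEs which were reported with 'action taken = Drug withdrawn' or 'action taken = Dose reduced". AEs are summarised by system organ class and preferred term. Table 7.8.1: 1 defines search concepts for infections, hypersensitivity, malignancies, peripheral neuropathy and others, but none for worsening of PPP.

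**Reason for stopping.** SAP 6.6.1 reports withdrawal reasons as entered on the eCRF. No readable text says whether a loss-of-response stop is to be entered as an AE or as lack of efficacy.

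**The concern.** PPP is chronic, patients enter improved, and follow-up lasts up to five years, so relapse is foreseeable. Each recorded relapse is a TEAE. If it also ends treatment and the site enters drug withdrawn as the action taken, it appears in the lines most often read as tolerability.

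There is no control arm against which to judge how much of an AE-discontinuation proportion is returning disease. Protocol 7.2.7 and SAP 3 foresee interim outputs for submissions, investigator brochure updates and publications, so the totals may be read well before the final report. At stake is the interpretation of the main safety summary. No error rate is affected, because the trial tests no hypothesis.

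**Working it through.** The documents state no expected TEAE, relapse or AE-discontinuation rate, so there is no planned figure to reproduce. The check has two parts: whether the totals can be unmixed from the planned tables, and how far they could move under assumed rates.

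**1. Can the totals be unmixed?** Let A be the patients with any TEAE and P the patients in the PPP rows. Some of the P patients will also have another TEAE. The number with a non-PPP TEAE therefore lies anywhere between A − P and A, and the table does not say where. The exposure-adjusted rate has a further obstacle. SAP 7.8.1 ends time at risk at onset of the event, so a patient whose first TEAE is PPP worsening leaves the denominator at that date. Neither the count nor the rate can be recovered by subtracting a row.

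The discontinuation table is different. A patient stops treatment once, often for one AE, so subtraction may come close there, provided the terms used for relapse are identifiable.

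**2. AE discontinuation (all rates assumed).** Take constant hazards per year: d for stops due to other AEs, r for relapse stops, o for other dropout. Let f be the share of relapse stops coded as an AE with drug withdrawn. Then:

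- 5-year AE discontinuation = [(d + f·r) / (d + r + o)] × [1 − exp(−5(d + r + o))]
- PPP share of AE discontinuations = f·r / (d + f·r)

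Central case: d = 0.02, r = 0.10, o = 0.10. The total hazard is 0.22 and 1 − exp(−1.1) = 0.667. N = 500 is the expected enrolment in Protocol 7.5.

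| f | Calculation | 5-year AE discontinuation | Patients of 500 | PPP share |
|---|---|---|---|---|
| 0 | 0.020/0.22 × 0.667 | 6.1% | 30 | 0% |
| 25% | 0.045/0.22 × 0.667 | 13.6% | 68 | 56% |
| 50% | 0.070/0.22 × 0.667 | 21.2% | 106 | 71% |
| 100% | 0.120/0.22 × 0.667 | 36.4% | 182 | 83% |

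Across d = 1 to 4% and r = 5 to 20% per year, with o = 10%, the two ends are:

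- d = 4%, r = 5%: 12.9% with relapse kept out; 16.9% at f = 25% and 29.0% at f = 100%.
- d = 1%, r = 20%: 2.5% with relapse kept out; 15.2% at f = 25% and 53.4% at f = 100%.

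Over this grid, with f from 25% to 100%, the PPP share runs from 24% to 95%.

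**3. Any-TEAE rate (all rates assumed).** With constant, independent hazards for the first non-PPP TEAE and for PPP worsening, the rate per 100 patient-years is the sum of the two.

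- Smallest effect: 200 + 5 = 205, which is +2.5%.
- Largest effect: 50 + 20 = 70, which is +40%.

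**The case against.** Much of the separation is already planned. Preferred-term rows would show PPP. SAP 7 gives disposition by reason and cumulative status every 16 weeks, with rescue intake among those who stopped and those ongoing. SAP 7.2 summarises rescue separately. Drug-related AEs, SAEs and AESIs have their own tables, and individual values are listed. The sponsor's AE standards cited in SAP 7.8.1, and the SAP text on rescue, cannot be read here and may hold a handling rule. The trial is descriptive, and Protocol 3.2 already acknowledges selection and reporting bias.

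This stands as a limit on the consequence: a careful reader can separate part of the mixture, most easily in the discontinuation table. It does not dispose of the point, because none of these outputs recomputes the any-TEAE count or rate.

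Three stronger readings are tempting but unsupported:

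- **That AE discontinuation will mainly reflect relapse.** A reader might add 5% other-AE stops to 20 to 40% relapse stops, get 25 to 45%, and call it 5 to 9 times the tolerability figure. Those rates are not in the documents. The sum needs every relapse stop to be coded as an AE, which no readable text requires. It also assumes no overlap, in which case subtracting the PPP row would recover the 5%.
- **That any loss of response forces a stop.** Only the two routes in Protocol 3.3.4.2 are mandatory. Perceived loss of benefit is the patient's choice under Protocol 3.3.4.1: "This includes patients losing individual perceived health benefit or becoming aware of a preferred treatment option".
- **That the efficacy results are contaminated.** The secondary endpoints are PPP ASI and PPP PGA measures, not AE counts.

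**Conclusion.** The point holds in a limited form. Mixing in the any-TEAE endpoint and its rate follows directly from the AE definition. Mixing in AEs leading to discontinuation and other significant AEs is conditional on how sites code action taken, which the readable documents leave open. That same openness means similar relapses could be classified differently between sites.

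The size cannot be known from the documents. The calculations show only sensitivity: in the central case, coding practice alone moves the discontinuation line about 2.2-fold at 25% coding (13.6/6.1) and about 6-fold at 100% (36.4/6.1). They rest on constant hazards and assumed rates. The any-TEAE rate is less sensitive. No planned analysis becomes invalid. This is an inexpensive improvement to how the safety totals can be read.

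**What to change.** In SAP 7.8.1 and Table 7.8.1: 1:

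1. Add a PPP-worsening search concept with a preferred-term list fixed before database lock, and before any interim snapshot that is reported.
2. Show the overall TEAE summary (frequency and exposure-adjusted rate), AEs leading to discontinuation and other significant AEs both including and excluding that concept. In the excluding version of the rate, time at risk should run to the first TEAE outside the concept, or otherwise to the SAP's existing censoring date.
3. Report PPP worsening as its own line.

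If a sponsor standard already covers this, citing it in SAP 7.8.1 would settle the matter.

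The primary endpoint definition, site AE recording and clinical management stay as they are. The cost is SAP wording, a short term list and a few repeated summary lines. The drawback is two versions of some totals side by side, which need clear labels.

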#### 5.2.6.1.2 Serious adverse event

A serious adverse event (SAE) is defined as any AE, which fulfils at least one of the following criteria:

- results in death,
- is life-threatening, which refers to an event in which the patient was at risk of death at the time of the event; it does not refer to an event that hypothetically might have caused death if more severe,
- requires inpatient hospitalisation or prolongation of existing hospitalisation
- results in persistent or significant disability or incapacity,
- is a congenital anomaly / birth defect,
- is deemed serious for any other reason if it is an important medical event when based on appropriate medical judgement which may jeopardise the patient and may require medical or surgical intervention to prevent one of the other outcomes listed in the above definitions. Examples of such events are intensive treatment in an emergency room or at home for allergic bronchospasm, blood dyscrasias or convulsions that do not result in hospitalisation or development of dependency or abuse.

For Japan only: the following events will be handled as “deemed serious for any other reason”. AEs which possibly lead to disability will be reported as SAEs.

#### 5.2.6.1.3 AEs considered “Always Serious”

In accordance with the European Medicines Agency initiative on Important Medical Events, Boehringer Ingelheim has set up a list of AEs, which by their nature, can always be considered to be “serious” even though they may not have met the criteria of an SAE as defined above.

The latest list of “Always Serious AEs” can be found in the EDC system. A copy of the latest list of “Always Serious AEs” will be provided upon request. These events should always be reported as SAEs as described in [Section 5.2.6.2](#).

Cancers of new histology and exacerbations of existing cancer must be classified as a serious event regardless of the time since discontinuation of the drug and must be reported as described in [Section 5.2.6.2](#), subsections “AE Collection” and “**AE reporting to sponsor and timelines**”.

#### 5.2.6.1.4 Adverse events of special interest

The term adverse events of special interest (AESI) relates to any specific AE that has been identified at the project level as being of particular concern for prospective safety monitoring and safety assessment within this trial, e.g. the potential for AEs based on knowledge from other compounds in the same class. AESIs need to be reported to the sponsor’s Pharmacovigilance Department within the same timeframe that applies to SAEs, please see [Section 5.2.6.2.2](#).

The following are considered as AESIs:

##### Systemic hypersensitivity reactions including anaphylactic reaction

Any suspicion of severe systemic hypersensitivity reaction and of any potential cases of anaphylaxis should be defined and assessed using the criteria discussed in the statement paper from Sampson HA ([Appendix 10.2, R11-4890](#)).

##### Severe infections (according to RCTC grading in [Appendix 10.3](#))

##### Opportunistic and mycobacterium tuberculosis infections

These include pneumocystis jirovecii, BK virus disease including PVAN, CMV, post-transplant lymphoproliferative disorder (EBV), progressive multifocal leucoencephalopathy, bartonellosis (disseminated only), blastomycosis, toxoplasmosis, coccidioidomycosis, histoplasmosis, aspergillosis (invasive only), candidiasis (invasive or pharyngeal), cryptococcosis, other invasive fungi (mucormycosis (zygomycosis, rhizopus, mucor, lichtheimia), scedosporium/pseudallescheria boydii, fusarium), legionellosis, listeria monocytogenes (invasive only), tuberculosis, nocardiosis, non-tuberculous mycobacterium, salmonellosis (invasive only), HBV reactivation, herpes simplex (invasive only), herpes zoster, strongyloides (hyperinfection syndrome and disseminated forms only), paracoccidioides, penicillium marneffeii, sporothrix schenckii, cryptosporidium species (chronic only), microsporidiosis, leishmaniasis (visceral only), trypanosoma cruzi infection (Chagas’ disease) (disseminated only), campylobacteriosis (invasive only), shigellosis (invasive only), vibriosis (invasive due to vibrio vulnificus), HCV progression [[R17-2617](#)].

### Hepatic injury

A hepatic injury is defined by the following alterations of hepatic laboratory parameters:

- an elevation of AST (Aspartate Aminotransferase) and/or ALT (Alanine Aminotransferase)  $\geq 3$  fold ULN combined with an elevation of total bilirubin  $\geq 2$  fold ULN measured in the same blood draw sample, or
- aminotransferase (ALT, and/or AST) elevations  $\geq 10$  fold ULN.

These lab findings constitute a hepatic injury alert and the patients showing these lab abnormalities need to be followed up according to the “DILI checklist” provided in the ISF.

In case of clinical symptoms of hepatic injury (icterus, unexplained encephalopathy, unexplained coagulopathy, right upper quadrant abdominal pain, etc.) without lab results (ALT, AST, total bilirubin) available, the investigator should make sure these parameters are analysed, if necessary in an unscheduled blood test. Should the results meet the criteria of hepatic injury alert, the procedures described in the DILI checklist should be followed.

